## **Site's Role in Assessing Severity and Causality of Adverse Events**

Appropriately qualified and trained study personnel will conduct an initial assessment of seriousness, severity, and causality when eliciting participant reporting of adverse events. A study medical clinician will review reportable AEs for seriousness, severity, and causality on at least a weekly basis.

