### **7.9.2 Maintenance of the Blind**

The individuals blinded to the study condition will be those conducting the study assessments. The baseline assessment will be blinded given that the randomization will not be revealed until after the assessment is completed. The follow up assessments will be conducted by a blinded research assistant.

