## **8.2 Clinical and Safety Assessments**

### **8.2.1 Adverse Events (AEs) and Serious Adverse Events (SAEs)**

At each visit the study navigator assesses for AEs and SAEs by asking the study participant, "How have you been feeling since your last visit?" AEs and SAEs may also be spontaneously reported to study staff at any visit following consent. AEs and SAEs suggesting medical or psychiatric deterioration will be brought to the attention of a study clinician for further evaluation and management. Visits will emphasize overdose risk and risk-management. Any reported overdose is recorded as an AE or SAE, or in a separate form. AE and SAE reporting is according to the reporting definitions and procedures outlined in the protocol and in accordance with applicable regulatory requirements.

For the purpose of this study, the following AEs do not require reporting in the data system but is captured in the source documentation as medically indicated:

Grade 1 (mild) unrelated adverse events. This would typically include mild physical events such as headache, cold, etc., that were considered not reasonably associated with the study intervention.

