#### **B. Medical Monitor**

The site study clinician is responsible for reviewing all adverse events and serious adverse events reported. All SAEs will be reviewed at the time they are reported data capture program. The site clinician will also indicate concurrence or not with the details of the report provided by the site PI. Where further information is needed, the study clinician will discuss the event with the site staff. All AEs are reviewed on a regular basis to observe trends or unusual events.

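### The staff member who elicits an adverse event can exempt it from entry as mild and unrelated with no clear clinician check; in the navigation arm that person is mostly the navigator

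*Combined protocol and SAP*

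**What the plan says.** Four statements form the chain.

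- **Who makes the first call.** Appendix A, on assessing severity and causality: "Appropriately qualified and trained study personnel will conduct an initial assessment of seriousness, severity, and causality when eliciting participant reporting of adverse events".
- **Who elicits.** Section 8.2.1: "At each visit the study navigator assesses for AEs and SAEs by asking the study participant". The sentence is not limited to one arm. There is a second route: "AEs and SAEs may also be spontaneously reported to study staff at any visit following consent". Section 7.5 says that the navigator delivers the PN intervention.
- **What is exempt.** Section 8.2.1 states that "the following AEs do not require reporting in the data system" and then names the category: "Grade 1 (mild) unrelated adverse events". Such events stay in source documents as medically indicated. Appendix A, on eliciting and reporting, requires sites to enter only reportable events.
- **What the clinician reviews.** Appendix A: "A study medical clinician will review reportable AEs for seriousness, severity, and causality on at least a weekly basis".

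Other statements point to wider review. Section 12.0, part B, says that "The site study clinician is responsible for reviewing all adverse events and serious adverse events reported", and it closes by saying that all AEs are regularly looked at for trends, without naming a reviewer or a data source. Section 12.0, part A, has all AEs collected and reported by the investigators, but requires entry only of reportable ones. The causality guidelines in Appendix A put the causality question to the study medical clinician.

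On the research assessments, Section 7.9.2 states: "The follow up assessments will be conducted by a blinded research assistant".

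**The concern.** The two judgements that take an event out of the data system, mild and unrelated, are made first by the person who asked about it. The clinician review that would correct a wrong judgement is defined on the events that survive it. An event wrongly placed in the exempt category therefore has no clear path to the person meant to check it.

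In PN this person is usually the navigator, who is asked in effect whether their own work caused harm. That is an interested rater, however well trained. In standard care there are no navigator sessions, and the documents do not say who elicits events. If it is the blinded research assistant, that person cannot soundly judge relatedness to the study intervention without knowing the arm.

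At stake are the data behind the benefit-to-risk decision in Section 12.0, part C, and the AE listings sent to the DSMB under the same section and Appendix A.

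**Working it through.** The plan gives no AE rate, AE count or planned harm comparison, so there is no figure to reproduce. The check has three parts.

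**1. The route of one event.** Suppose an event is elicited at a PN session and called Grade 1 and unrelated.

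- Section 8.2.1: it need not be entered.
- Appendix A, eliciting and reporting: it is not reportable, so the 7-day entry rule and the study PI's review on submission do not apply.
- Appendix A, assessing severity and causality: it is outside the weekly clinician review.
- Section 12.0, part B: the opening sentence covers reported events; the closing sentence covers all AEs, but it is not clear who would see an event held only in source.
- Appendix A, causality guidelines: the clinician answers the causality question, yet the exemption already depends on an answer to it.

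Now change one judgement. If the event is called related, or Grade 2 or 3, or serious, it is reportable, is entered, and reaches the clinician. The gap is confined to events called both Grade 1 and unrelated.

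**2. How often the navigator is the contact in PN.** Inputs: up to 10 prenatal and 4 postnatal sessions, and 4 assessments of which 1 is baseline (Section 3.2). This takes the navigator as the contact at sessions and the research assistant at follow-up assessments. Calls and texts between sessions are not counted.

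- Sessions: 10 + 4 = 14. Follow-up assessments: 4 − 1 = 3. Total: 17.
- Navigator share: 14/17 = 82%.
- If only 4, 6 or 8 prenatal sessions are attended (assumption): 8/11 = 73%, 10/13 = 77%, 12/15 = 80%.
- Standard care: 3 scheduled contacts, none of them a navigator session.

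These are shares of contacts, not of events.

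**3. Which way the filter could push.** Assumptions, for illustration only: 61 women per arm (the planned arm size, Section 10.2.2), one non-serious AE each, the same true rate in both arms, a share g of events truly Grade 1, and every Grade 1 event in standard care called unrelated because no PN was given.

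- *Relatedness effect.* Let u be the share of Grade 1 events in PN called unrelated. Entered in standard care: 61 × (1 − g). Entered in PN: 61 × (1 − g × u). With g = 0.5, standard care enters 30.5. PN enters 30.5, 36.6 or 45.8 for u = 1, 0.8 or 0.5. The PN to standard-care ratio is 1.0, 1.2 or 1.5. With g from 0.3 to 0.7 and u from 0.5 to 1, it runs from 1.0 to 2.2.
- *Lenient grading in PN.* Let u = 1, and let a share m of the higher-grade PN events be graded down and called unrelated. The ratio is (1 − g)(1 − m)/(1 − g) = 1 − m, which is 0.9, 0.8 or 0.7 for m = 0.1, 0.2 or 0.3.

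The first effect raises recorded PN events relative to standard care, and the second lowers them.

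**The case against.** The strongest reply is that the elicitor's call is only initial. Seriousness is defined by the view of the medical clinician or sponsor, the causality question belongs to the clinician, and Section 12.0, part B, speaks of all AEs being reviewed. The personnel must be qualified and trained, and Section 9.1 includes safety event reporting in that training. The exempt category is illustrated by trivial complaints. Overdose, suicidality and signs of deterioration have their own routes (Sections 8.2.1 and 8.2.2), and monthly meetings review depression, drug use and treatment adherence. Section 10.3 plans no between-arm comparison of AEs, so no stated analysis is biased.

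Much of this stands, and it limits the consequence. It does not close the gap: the statements on wider review conflict with the weekly-review sentence, and none clearly sends an exempted event to a clinician.

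Three stronger readings are tempting, and the documents do not support them.

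- A reader might infer that any event called mild misses the 7-day deadline. It does not: a mild event called related is still reportable. An event wrongly called non-serious would miss the 24-hour deadline but, unless it is also called Grade 1 and unrelated, is still entered within 7 days and re-assessed weekly.
- A reader might infer that PN harms are removed while nothing comparable happens in standard care. The exemption is not specific to an arm, and Grade 1 events in standard care may leave almost by rule. Read literally, Section 8.2.1 even has the navigator asking in both arms, so the arm contrast is partly inference.
- A reader might multiply 82% by a misgrading rate to obtain a lost share of PN events. The documents give no such rate, and the 82% counts contacts.

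The remark in Section 1.1 that PN can be delivered by bachelors-level staff describes the model and is not evidence about this study's navigators.

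**Conclusion.** The point holds in a limited form. An event called both Grade 1 and unrelated by the person who elicited it need not be entered and is not clearly sent to a clinician. In PN, up to 14 of 17 scheduled contacts after randomisation (82%; 73% if four prenatal sessions are attended) are with the navigator, so an interested rater can apply this exemption unchecked.

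Recorded harms may therefore be filtered differently by arm within that one category. Neither the size nor the direction of a difference can be taken from the documents; the ratios above and below 1 rest on assumed shares. The contact shares rest on navigator sessions being confined to PN and on follow-up assessments being run by the research assistant. Who elicits AEs in standard care is not stated. The sentences on the scope of clinician review contradict one another and must be reconciled. A correction is worthwhile because the data inform safety decisions and the change is small.

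**What to change.** In Section 8.2.1 and Appendix A:

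- State that the elicitor's assessment is provisional, and that anything possibly serious is notified at once.
- State that the study medical clinician makes or confirms seriousness, severity and causality for every elicited AE, in both arms, at the existing weekly review, and that the Grade 1 unrelated exemption is applied only afterwards.
- In the weekly-review sentence of Appendix A, replace reportable AEs by all AEs, and align Section 12.0, parts A and B, and the causality guidelines with it.
- State who elicits AEs in each arm and at which visits, consistently with the blinding in Section 7.9.2.

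The cost is protocol and form wording, plus some additional mild events for the clinician each week. No new staff are needed. Grading with the arm concealed is not part of this change; it would be an added procedure.

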## Guidelines for Assessing Severity

The severity of an adverse event refers to the intensity of the event:

Grade 1	Mild	Transient or mild discomfort (typically < 48 hours), no or minimal medical intervention/therapy required, hospitalization not necessary (non-prescription or single-use prescription therapy may be employed to relieve symptoms, e.g., aspirin for simple headache, acetaminophen for post-surgical pain)
Grade 2	Moderate	Mild to moderate limitation in activity some assistance may be needed; no or minimal intervention/therapy required, hospitalization possible.
Grade 3	Severe	Marked limitation in activity, some assistance usually required; medical intervention/ therapy required, hospitalization possible.

## Guidelines for Determining Causality

The study medical clinician will use the following question when assessing causality of an adverse event to study medication/intervention where an affirmative answer designates the event as a suspected adverse reaction:

*Is there a reasonable possibility that the study intervention caused the event?*

## Reporting to the Data and Safety Monitoring Board

The DSMB will receive listing of AEs and summary reports of all SAEs at a frequency requested by the DSMB, but at least annually. Furthermore, the DSMB will be informed of expedited reports of SAEs.

## Participant Withdrawal

The study medical clinician must apply his/her clinical judgment to determine whether or not an adverse event is of sufficient severity to require that the participant be withdrawn from further study intervention. The study medical clinician should consult with the lead investigator as needed. If necessary, a study medical clinician may suspend any trial interventions and institute the necessary medical therapy to protect a participant from any immediate danger. A participant may also voluntarily withdraw from treatment due to what he/she perceives as an intolerable adverse event or for any other reason. If voluntary withdrawal is requested, the participant will be asked to complete an end-of-study visit to assure safety and will be given recommendations for medical care and/or referrals to treatment, as necessary.

